------------	------------	--------------------	--------------------	------------

Pacira Pharmaceuticals, Inc.
402-C-323

Listing 16.5.5
Sensitivity to Cold

Study Part: X Treatment Group: YYY

Subject ID	Time Point	Date of Assessment	Time of Assessment	Sensitivity to Cold
------------	------------	--------------------	--------------------	---------------------

Pacira Pharmaceuticals, Inc.
402-C-323

Listing 16.5.6
Predefined Treatment-Emergent Opioid-Related Adverse Events at 72 Hours (Study Part 1)

Study Part: X Treatment Group: YYY

Subject ID	Date of Assessment	Diffuse Pruritus	Overt Respiratory Depression	Urinary Retention [1]	Constipation	Sedation	Confusion	Delirium	Vomiting	Need for Antiemetic Medication
------------	--------------------	------------------	------------------------------	-----------------------	--------------	----------	-----------	----------	----------	--------------------------------

[1] Urinary retention was measured by need for postsurgical bladder catheterization.

Pacira Pharmaceuticals, Inc.
402-C-323

Listing 16.6.1
Scheduled Bupivacaine Plasma Concentrations (Study Part 1)

Treatment Group: YYY

Subject ID	Dose Time [1]	Date of Sample	Time of Sample	Time Point	Elapsed Time (hours) [2]	Total Bupivacaine Plasma Concentration (ng/mL)	Unbound Bupivacaine Plasma Concentration (ng/mL)
------------	------------------	-------------------	-------------------	------------	-----------------------------	---	--

[1] Dose time is the start time of study drug administration.

[2] Elapsed time is the time the sample was collected relative to the time of dose.

Pacira Pharmaceuticals, Inc.
402-C-323

Listing 16.6.2
Bupivacaine Plasma Pharmacokinetic Parameters (Study Part 1)

Treatment Group: YYY

Subject ID	Cmax (ng/mL)	Tmax (hours)	AUC 0-last (h*ng/mL)	AUC 0-inf (h*ng/mL)	t1/2 (hours)
------------	-----------------	-----------------	-------------------------	------------------------	-----------------

[1] Dose time is the start time of study drug administration.

[2] Elapsed time is the time the sample was collected relative to the time of dose.

Pacira Pharmaceuticals, Inc.
402-C-323

Listing 16.6.3
Unscheduled Bupivacaine Plasma Concentrations

Study Part XX Treatment Group: YYY

Subject ID	Dose Time [1]	Date of Sample	Time of Sample	Reason for Collection	Elapsed Time (hours) [2]	Bupivacaine Plasma Concentration (ng/mL)
------------	------------------	-------------------	-------------------	--------------------------	-----------------------------	---

[1] Dose time is the start time of study drug administration.

[2] Elapsed time is the time the sample was collected relative to the time of dose.

Pacira Pharmaceuticals, Inc.
402-C-323

Listing 16.7.1.1
Adverse Events (Part 1 of 2)

Study Part: X Treatment Group: YYY

Subject ID	SOC / Preferred Term / Verbatim Term	Start Date / Time	End Date / Time	Solicited From:		Serious	Severity	Relationship to Study Drug	Outcome
				Neuro. [1]	ORAE [2]				

* Indicates that the event is not treatment-emergent.

[1] Neurological assessment.

[2] Predefined treatment-emergent opioid-related adverse events questionnaire.

*Programmer note: If the subject has no adverse events, then put 'NONE' in the "SOC/Preferred Term/Verbatim Term" column.
Use formatted terms as much as possible. If you have to use codes, then add footnotes to explain the codes.*

Pacira Pharmaceuticals, Inc.
402-C-323

Listing 16.7.1.2
Adverse Events (Part 2 of 2)

Study Part: X Treatment Group: YYY

Subject ID	SOC / Preferred Term / Verbatim Term	Start Date / Time	End Date / Time	Action Taken with Subject				
				None	Medication	Non- Pharmaceutical Therapy	Discontinued from Study	Other

* Indicates that the event is not treatment-emergent.

*Programmer note: If the subject has no adverse events, then put 'NONE' in the "SOC/Preferred Term/Verbatim Term" column.
Use formatted terms as much as possible. If you have to use codes, then add footnotes to explain the codes.*

Pacira Pharmaceuticals, Inc.
402-C-323

Listing 16.7.1.3
Serious Adverse Events (Part 1 of 2)

Study Part: X Treatment Group: YYY

Subject ID	SOC / Preferred Term / Verbatim Term	Start Date / Time	End Date / Time	Solicited From:		Severity	Relationship to Study Drug	Outcome
				Neuro. [1]	ORAE[2]			

* Indicates that the event is not treatment-emergent.

[1] Neurological assessment.

[2] Predefined treatment-emergent opioid-related adverse events questionnaire.

*Programmer note: If the subject has no adverse events, then put 'NONE' in the "SOC/Preferred Term/Verbatim Term" column.
Use formatted terms as much as possible. If you have to use codes, then add footnotes to explain the codes.*

Pacira Pharmaceuticals, Inc.
402-C-323

Listing 16.7.1.4
Serious Adverse Events (Part 2 of 2)

Study Part: X Treatment Group: YYY

Subject ID	SOC / Preferred Term / Verbatim Term	Start Date / Time	End Date / Time	Action Taken with Subject				
				None	Medication	Non- Pharmaceutical Therapy	Discontinued from Study	Other

* Indicates that the event is not treatment-emergent.

*Programmer note: If the subject has no adverse events, then put 'NONE' in the "SOC/Preferred Term/Verbatim Term" column.
Use formatted terms as much as possible. If you have to use codes, then add footnotes to explain the codes.*

Pacira Pharmaceuticals, Inc.
402-C-323

Listing 16.7.1.5
Deaths

Study Part: X Treatment Group: YYY

Subject ID	Date of Death	Primary Cause	Autopsy Performed?	Report Obtained?
-------------------	----------------------	----------------------	-------------------------------	-----------------------------

Pacira Pharmaceuticals, Inc.
402-C-323

Listing 16.8
Height, Weight, and Vital Signs

Study Part: X Treatment Group: YYY

Subject ID	Time Point	Date of Assessment	Time of Assessment	Height (cm)	Weight (kg)	Heart Rate (bpm)	Blood Pressure (mmHg)	
							Systolic	Diastolic

Pacira Pharmaceuticals, Inc.
402-C-323

Listing 16.9
Neurological Assessment

Study Part: X Treatment Group: YYY

Subject ID	Time Point	Date of Assessment	Time of Assessment	Oriented	Numbness [1]	Metallic Taste in Mouth	Problems with Hearing	Problems with Vision	Muscles Twitching
------------	------------	--------------------	--------------------	----------	--------------	-------------------------	-----------------------	----------------------	-------------------

[1] Numbness of the lips, the tongue, or around the mouth.

Pacira Pharmaceuticals, Inc.
402-C-323

Listing 16.10
20-Meter Walk Test

Study Part: X Treatment Group: YYY

Subject ID	Time Point	Date of Assessment	Time of Assessment	Able to Perform the Test?	If No, Provide Reason
------------	------------	--------------------	--------------------	---------------------------	-----------------------

Pacira Pharmaceuticals, Inc.
402-C-323

Listing 16.11
Physician Satisfaction with Return of Sensory/Motor Function

Study Part: X Treatment Group: YYY

Subject ID	Time Point	Date of Assessment	Time of Assessment	Assessment
------------	------------	--------------------	--------------------	------------

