15.6.3.1 Primary Efficacy Measure

The primary efficacy measure in this study is the AUC of the NRS-R pain intensity scores through 72 hours.

Handling of Subjects Requiring Rescue Medication

For AUC of the NRS-R and NRS-A pain intensity scores, prior to analysis the windowed Worst-Observation-Carried-Forward (wWOFCF) imputation method will be applied. For subjects who take rescue pain medication, their pain intensity scores recorded within the window of controlled type of rescue medication (6 hours for oxycodone, 4 hours for morphine, and 2 hours for IV hydromorphone) will be replaced by the ‘worst’ observation. For subjects who require a rescue with conventional bupivacaine HCl, the window will be from the start of the bupivacaine infusion until the end of the infusion plus 12 hours. All pain scores within that window will be replaced by the ‘worst’ observation. The worst observation will be the highest score in the time interval from the end of surgery up to the time prior to taking their first rescue pain medication. Note that pain intensity scores in the window that are higher than the worst value prior to rescue pain medication will not be overwritten. If no pain intensity score is available prior to the first rescue pain medication, the worst observation from all available measurements will be used instead.

Part 1

For AUC of the NRS-R pain intensity scores through 72 hours, each dose of liposome bupivacaine will be compared to placebo using analysis of covariance (ANCOVA) with treatment as the main effect and the baseline NRS-R pain intensity score as the covariate. Based on the model, the difference between each dose of liposome bupivacaine and placebo will be estimated along with the 2-sided 95% confidence interval (CI).

Part 2

For AUC of the NRS-R pain intensity scores through 72 hours, liposome bupivacaine will be compared to placebo using ANCOVA with treatment as the main effect and the baseline NRS-R pain intensity score as the covariate. Based on the model, the difference between the treatment groups will be estimated along with the 2-sided 95% CI.

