7. STATISTICAL METHODS OF ANALYSIS

7.1. General Principles

Descriptive statistics (the number of subjects [n], mean, standard deviation [SD], median, minimum, and maximum) will be used to summarize continuous variables. Means and medians will be presented to one more decimal place than the recorded data. Standard deviations will be presented to two more decimal places than the recorded data. Minimum and maximum values will be presented using the same number of decimal places as the recorded data. Percentages will be presented to one decimal place.

In addition, for PK parameters, geometric means and between-subject coefficient of variations (%CV) will be presented.

Frequency distributions (number [n] and percentage of subjects [%]) will be used to summarize categorical or qualitative variables. In general, the denominator for the percentage calculation will be based upon the total number of subjects in the study population for the treatment groups, unless otherwise specified.

All statistical tests will be performed against a two-sided alternative hypothesis with a significance level of 5% ($\alpha = 0.05$), and all confidence intervals (CIs) calculated will be two-sided 95% CIs. All tests will be declared to be statistically significant if the calculated p-value is ≤ 0.05 unless specified otherwise. Tests for binomial proportions will be conducted (1) using a normal approximation whenever each classification cell for each group to be compared contains expected cell counts of 5 or more subjects, or (2) using an exact method whenever any one classification cell for any one group to be compared contains expected cell counts of fewer than 5 subjects.

All analyses will be performed using SAS[®] Software version 9.2 or later.

Pharmacokinetic parameters will be derived using noncompartmental methods with WinNonlin[®] Professional Version 5.2 or later (Pharsight Corp., Cary, North Carolina).

For the listings, subjects will be listed under their randomized treatment, regardless of actual treatment received. Subjects who are randomized but do not receive study drug will be included in the listings with the treatment group identified as “Liposome bupivacaine xx mg, Not Treated” or “Placebo, Not Treated”, depending on their randomized treatment.

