7.1.2. Imputation of NRS Pain Intensity Scores

For calculation of AUC of NRS pain intensity scores, the windowed worst observation carried forward (wWOCF) and last observation carried forward (LOCF) imputation procedure will be used as follows:

- a) Windowed worst observation carried forward for rescue medications

For subjects who take a rescue medication, their NRS scores recorded within the window of controlled type of rescue medication (see the table below for the windows for the planned rescue medications) will be replaced by the ‘worst’ observation. The worst observation will be the highest score in the time interval from Time 0 to up to the time prior to taking the first rescue medication. The NRS score at the first rescue will be included in this calculation. Note that NRS scores in the window that are higher than the worst value prior to rescue medication will not be overwritten. If no NRS score is available prior to the first rescue the worst observation from all available NRS scores will be used instead.

Medication	Route	Window Used to Impute NRS
Oxycodone	PO	6 hours
Oxycontin (MS Contin)	PO	6 hours
Morphine	IV	4 hours
Hydromorphone (Dilaudid)	IV	2 hours
Hydromorphone (Dilaudid)	PO	4 hours
Fentanyl	IV	6 hours
Fentanyl	Transdermal	Start of administration until the end of the administration plus 6 hours
Hydrocodone	PO	6 hours
Bupivacaine HCl	Perineural	12 hours
Bupivacaine HCl	Infusion	Start of the infusion until the end of the infusion plus 12 hours

Ropivacaine		Start of the infusion until the end of the infusion plus 12 hours
Meperidine	IV	4 hours
Ultram	PO	6 hours

IV = intravenous; PO = oral.

If unplanned rescue medications are given then the window will be determined post-hoc prior to breaking the blind. If a combination opioid is given then the window will be determined by the opioid part of the medication. Opioids given postsurgically with an indication like ‘anesthesia maintenance’ will not be included for imputation purposes.

- b) Missing scores before the first non-missing score will be replaced by the median score at the missing time point from the other subjects in the same treatment group.
- c) Missing scores after the last non-missing score will be replaced by the LOCF.
- d) Missing scores between two non-missing scores will not be replaced (i.e., linear interpolation will be used).

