7.6.2.3 Tertiary Efficacy Variables

For Part 1, no statistical tests will be performed on any of the tertiary efficacy variables. Only descriptive statistics will be shown for each treatment.

For Part 2, the following describes the statistical analyses to be performed.

NRS-R, NRS-A, and AUC of Pain Intensity Scores

For the tertiary efficacy variables NRS-R, NRS-A, and the AUCs of the NRS-R and NRS-A pain intensity scores, the same analyses as those for the primary efficacy variable will be performed, except that the baseline NRS-A score will be used as the covariate for all variables using the NRS-A.

Proportion of Subjects Who are Pain Free

Pain free is defined as an NRS-R pain intensity score of 0 or 1. The number and percentage of subjects who are pain free will be summarized by treatment group for each time point. A chi-square test will be used to compare liposome bupivacaine to placebo.

Total Postsurgical Opioid Consumption Through 24, 36, 48, and 60 Hours

For the tertiary efficacy variables total opioid consumption through each of the time periods, the same analysis as that for the secondary efficacy variable of total opioid consumption through 72 hours will be performed.

Subjects Who Receive Rescue Medication

The category of ‘Subjects who receive no rescue medication’ is defined as subjects who report not taking any medication on the four Rescue Medication eCRFs.

The category of ‘Subjects who only receive the IV hydromorphone bolus’ is defined as subjects who report taking IV hydromorphone (or other opioid medications) on the First Rescue Medication eCRF and report not taking a medication on either of the Second Rescue Medication eCRFs or on the Third Rescue Medication eCRF.

The category of ‘Subjects who receive the IV hydromorphone bolus and a second opioid medication’ is defined as subjects who report taking IV hydromorphone (or other opioid medication) on the First Rescue Medication eCRF and who report taking a medication on either of the Second Rescue Medication eCRFs and report not taking a medication on the Third Rescue Medication eCRF.

The category of ‘Subjects who receive the IV hydromorphone bolus, a second opioid medication, and conventional bupivacaine HCl’ is defined as subjects who report taking IV hydromorphone (or other opioid medication) on the First Rescue Medication eCRF, who report taking a medication on either or both of the Second Rescue Medication eCRFs, and bupivacaine HCl on the Third Rescue Medication eCRF.

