402-C-323

Table 14.2.2.3.2 (Page x of Y)
Time to First Opioid Rescue
Study Part 2
(Efficacy Analysis Set)

	LB XXX mg (N=XX)	Placebo (N=XX)
Subjects Administered an Opioid Rescue [n (%)]	00 (00.00)	00 (00.00)
Censored Observations [n (%)]	00 (00.00)	00 (00.00)
Quartiles (hours) [1]		
First Quartile (25% Administered an Opioid)	000	000
Median (50% Administered an Opioid)	000	000
Third Quartile (75% Administered an Opioid)	000	000
Minimum, Maximum	00, 00*	00, 00*
95% CI of Median	(000, 000)	(000, 000)
P-value from Log-Rank Test	0.0000	0.0000

* indicates a censored observation.

CI = confidence interval; LB = liposome bupivacaine.

[1] Estimates from a Kaplan-Meier Analysis.

Reference: [Listing 16.5.2.1](#).

Pacira Pharmaceuticals, Inc.
402-C-323

Table 14.2.2.4-2 (Page x of Y)
NRS-R Pain Intensity Scores
Study Part 2
(Efficacy Analysis Set)

Time Point	Statistics	LB XXX mg (N=XX)	Placebo (N=XX)
Baseline	n	00	00
	Mean	000.0	000.0
	SD	00.00	00.00
	Median	0000	0000
	Minimum, Maximum	000, 000	000, 000
First Request	n	00	00
	Mean	000.0	000.0
	SD	00.00	00.00
	Median	0000	0000
	Minimum, Maximum	000, 000	000, 000
	LSM (Standard Error) [1]	00.0 (00.00)	00.0 (00.00)
	LSM Difference (Standard Error) [2]	00.0 (00.00)	
	95% CI for Difference [2]	00.0, 00.0	
	P-value [2]	0.0000	
2 Hours	n	00	00
	Mean	000.0	000.0
	SD	00.00	00.00
	Median	0000	0000
	Minimum, Maximum	000, 000	000, 000

Etc.

CI = confidence interval; LB = liposome bupivacaine; LSM = least squares mean; NRS-R = numeric rating scale at rest.

Scores are based on a numeric rating scale where 0 = no pain and 10 = worst possible pain.

[1] From an analysis of covariance with treatment as the main effect and the baseline NRS-R pain intensity score as the covariate.

[2] Difference from placebo.

Reference: [Listing 16.5.1.1.](#)

Pacira Pharmaceuticals, Inc.
402-C-323

Table 14.2.2.5-2 (Page x of Y)
NRS-A Pain Intensity Scores
Study Part 2
(Efficacy Analysis Set)

Time Point	Statistics	LB XXX mg (N=XX)	Placebo (N=XX)
Baseline	n	00	00
	Mean	000.0	000.0
	SD	00.00	00.00
	Median	0000	0000
	Minimum, Maximum	000, 000	000, 000
First Request	n	00	00
	Mean	000.0	000.0
	SD	00.00	00.00
	Median	0000	0000
	Minimum, Maximum	000, 000	000, 000
	LSM (Standard Error) [1]	00.0 (00.00)	00.0 (00.00)
	LSM Difference (Standard Error) [2]	00.0 (00.00)	
	95% CI for Difference [2]	00.0, 00.0	
	P-value [2]	0.0000	
	2 Hours	n	00
Mean		000.0	000.0
SD		00.00	00.00
Median		0000	0000
Minimum, Maximum		000, 000	000, 000
Etc.			

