8 Hours	00/00 (00.0)	00/00 (00.0)	0.0000
12 Hours	00/00 (00.0)	00/00 (00.0)	0.0000
24 Hours	00/00 (00.0)	00/00 (00.0)	0.0000
36 Hours	00/00 (00.0)	00/00 (00.0)	0.0000
Etc			

LB = liposome bupivacaine. n/N = Number of subjects with a pain score of 0 or 1 / Number of subjects with a pain score at the time point.

Pain Free is defined as an NRS-R pain intensity score of 0 or 1

[1] P-value is from a chi-square test.

Reference: [Listing 16.5.1.1](#).

Pacira Pharmaceuticals, Inc.
402-C-323

Table 14.2.2.10-2 (Page x of Y)
Total Postoperative Consumption (mg) of Opioid Rescue Pain Medication Through 24, 36, 48, and 60 Hours
Study Part 2
(Efficacy Analysis Set)

Time Point	Statistics	LB 67 mg (N=XX)	Placebo (N=XX)
24 Hours	n	00	00
	Mean	00.00	00.00
	SD	00.000	00.000
	Median	00.00	00.00
	Minimum, Maximum	00.0, 00.0	00.0, 00.0
	Geometric LSM [1]	00.00	00.00
	Geometric LSM Ratio [2]	00.00	
	95% CI for Ratio [2]	00.00, 00.00	
	P-value [2]	0.0000	
Etc.			

CI = confidence interval; LB = liposome bupivacaine, LSM = least squares mean.

If the total amount of opioid used was 0 mg, the value was set to the lesser of 1 mg or one half of the smallest total amount observed in the study prior to being transformed into the natural logarithm.

[1] From an analysis of variance with treatment as the main effect on natural log transformed opioid amount.

Results are presented in the original, non-transformed scale.

[2] Geometric LSM ratio is the anti-log LSM difference (LB/placebo).

Reference: [Listing 16.5.2.1](#).

Pacira Pharmaceuticals, Inc.
402-C-323

Table 14.2.2.11-2 (Page x of Y)
Subjects Who Received Rescue Medication Through 72 Hours
Study Part 2
(Efficacy Analysis Set)

	LB XXX mg (N=XX) n (%)	Placebo (N=XX) n (%)	P-value [1]
Received No Rescue Medication	00 (00.0)	00 (00.0)	
Received Only the First Rescue	00 (00.0)	00 (00.0)	
Received the First Rescue and a Second Opioid Rescue	00 (00.0)	00 (00.0)	
Received all Three Rescues	00 (00.0)	00 (00.0)	

LB = liposome bupivacaine.

[1] P-value is from a chi-square test

Reference: [Listings 16.5.2.1](#) and [16.5.2.2](#).

Pacira Pharmaceuticals, Inc.
402-C-323

Table 14.2.2.12-2 (Page x of Y)
Overall Benefit of Analgesia Score Questionnaire (Total Scores)
Study Part 2
(Efficacy Analysis Set)

Time Point	Statistics	LB XXX mg (N=XX)	Placebo (N=XX)	P-value [1]
24 Hours	n	00	00	0.0000
	Mean	000.0	000.0	
	SD	00.00	00.00	
	Median	0000	0000	
	Minimum, Maximum	000, 000	000, 000	
48 Hours	n	00	00	0.0000
	Mean	000.0	000.0	

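### Two Part 2 tertiary comparisons, the first-rescue-request pain score and the pain-free proportion, are tested on subsets formed after randomisation

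*SAP*

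**What the plan says.** **First request.** Protocol 12.1 and 13.5 collect NRS-R and NRS-A when a subject first asks for rescue, if that happens. SAP 7.6.2.3 applies the primary ANCOVA to the NRS scores. The shells for Tables 14.2.2.4-2 (NRS-R) and 14.2.2.5-2 (NRS-A) include a "First Request" row with least squares means, their difference, a 95% CI and a p-value.

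**Pain-free denominator.** SAP 7.6.2.3 states: "A chi-square test will be used to compare liposome bupivacaine to placebo". Table 14.2.2.9-2 carries the Efficacy Analysis Set label, but its footnote defines n/N as "Number of subjects with a pain score of 0 or 1 / Number of subjects with a pain score at the time point". SAP 7.1 gives the default: "In general, the denominator for the percentage calculation will be based upon the total number of subjects in the study population". That sentence ends by allowing exceptions where otherwise specified.

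**Pain-free definition.** "Pain free is defined as an NRS-R pain intensity score of 0 or 1". There is no condition on rescue.

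**Scope of imputation.** SAP 7.1.2 opens "For calculation of AUC of NRS pain intensity scores, the windowed worst observation carried forward (wWOCF) and last observation carried forward (LOCF) imputation procedure", and protocol 15.6.3.1 likewise begins "For AUC of the NRS-R and NRS-A pain intensity scores, prior to analysis the windowed Worst-Observation-Carried-Forward". Protocol 15.5 restricts its missing-score rules to the AUC too. Nothing fills in or replaces a score for the pain-free table.

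**Withdrawal.** Under the protocol synopsis and 9.1, subjects without adequate relief after the rescue sequence leave the study and are followed for adverse events only.

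**The concern.** A first-request score exists only because the subject asked for rescue. Time to first opioid rescue is a secondary endpoint, so the design itself expects treatment to change whether and when subjects ask. The row compares requesters on active with requesters on placebo, at times that treatment may have shifted. Randomisation does not protect that comparison, and its p-value has no clear meaning.

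The pain-free test has the same weakness in milder form. A subject withdrawn for uncontrolled pain is a plain analgesic failure, yet is absent from every later denominator. If such withdrawals differ by arm, the compared groups differ for reasons related to outcome.

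A third feature is of another kind. A subject scoring 1 shortly after a PCA dose is a success in the pain-free table, while the primary AUC replaces that score whenever the worst pre-rescue score is higher. The two analyses can then give different pictures of the same scores, and the SAP does not say this is intended.

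**Working it through.** **The plan's own figure.** Protocol 15.3 and SAP 8 state more than 97% power for the primary AUC: difference 61, SD 104, 90 per arm, two-sided 0.05. Then 61 / (104 × √(2/90)) = 3.935, and Φ(3.935 − 1.960) = 97.6%; the noncentral t with 178 df gives 97.5%. The figure reproduces and this point does not touch it. The documents give no figure for the tests below, so every rate that follows is an assumption.

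**Which scores feed the pain-free table.** Listing 16.5.1.1 has actual and imputed score columns, and the table does not name one. The imputation is limited to the AUC, and carrying scores forward would leave no late gaps for a scores-available denominator to handle. Actual scores are therefore the natural reading.

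**(a) First request.** Assumed: no treatment effect on the score, score SD 2, and a request made when score plus noise (SD 2) passes a threshold set to give the stated request rate; 90 randomised per arm; unadjusted comparison of means. Simulated results against a nominal 5%:

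| Request rate, active v placebo | Spurious difference | Rejection probability |
|---|---|---|
| 95% v 100% | 0.15 | 8% |
| 90% v 100% | 0.27 | 15% |
| 80% v 95% | 0.34 | 21% |
| 70% v 95% | 0.55 | 45% |

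With equal request rates in this model the rejection probability is 5%.

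**(b) Denominator.** Uncorrected Pearson chi-square, 27 active and 15 placebo successes:

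- 27/90 v 15/90: p = 0.034
- 27/90 v 15/85: p = 0.056
- 27/90 v 15/80: p = 0.090
- 27/90 v 15/75: p = 0.142
- 27/90 v 15/70: p = 0.222

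The direction follows the assumed dropouts. Losing 10 from each arm (27/80 v 15/80) gives z = 0.150 / √(0.2625 × 0.7375 × 2/80) = 2.16, p = 0.031. Losing 10 from active only (27/80 v 15/90) gives z = 0.1708 / √(0.2471 × 0.7529 × (1/80 + 1/90)) = 2.58, p = 0.010.

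**(c) Score-only definition.** Power = Φ[(d − 1.96 × SE₀) / SE₁], where d is the difference, SE₀ = √(2p̄(1 − p̄)/90) and SE₁ = √([p₁(1 − p₁) + p₂(1 − p₂)]/90). For 20% v 30%, SE₀ = 0.0645 and SE₁ = 0.0641, so power = Φ(−0.41) = 34%. Counting in-window successes as failures:

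| Share of successes in a window, placebo / active | Proportions, placebo v active | Power |
|---|---|---|
| none | 20% v 30% | 34% |
| one fifth / one fifth | 16% v 24% | 27% |
| two fifths / two fifths | 12% v 18% | 20% |
| one half / one fifth | 10% v 24% | 71% |

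The answer turns on the split between arms, which the documents do not give.

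**The case against.** The strongest reply is that these are tertiary variables outside the testing hierarchy in SAP 7.1.4, so no primary or secondary conclusion can change. Missing scores are not hidden either: the table prints n/N at each time point, and disposition lists lack of efficacy by arm. Withdrawal for pain comes only after the rescue sequence fails, in subjects who stay on site for at least 72 hours, so few may be lost. All of this stands and keeps the point minor. It does not supply a reason to drop analgesic failures or to test a requester-only score.

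On rescue, both documents confine the worst-observation rule to the AUC and report rescue separately through opioid consumption, time to first rescue and the rescue categories. Reported pain regardless of rescue is a legitimate quantity. This stands too, and is why a rescue-adjusted proportion belongs beside the raw one, not in its place. PCA interval data also make some windows approximate: SAP 7.1.3 assumes doses at the start, middle and end of an interval, and SAP 7.6.2.1 excludes those subjects in a sensitivity analysis.

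Four stronger readings are tempting, and the documents do not support them:

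- That the footnote contradicts SAP 7.1. The default yields where otherwise specified, and the footnote specifies otherwise.
- That all opioid-treated subjects count as successes. Only those scoring 0 or 1 do.
- That ignoring rescue makes a post-randomisation subset. Every scored subject stays in.
- That the pain-free rules must favour placebo and conceal a real effect. That needs more withdrawal and rescue on placebo, for which no rates are given.

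**Conclusion.** The point holds for two displays. The first-request p-values in Tables 14.2.2.4-2 and 14.2.2.5-2 do not compare randomised groups. The pain-free tests in Table 14.2.2.9-2 let withdrawals for inadequate relief disappear from the denominator. The score-only definition is a separate matter of estimand that the SAP should state openly.

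Size and direction cannot be fixed from the documents. Under the assumed ranges, testing at first request rejects 8% to 45% of the time with no true effect on the score. The denominator rule moves p from 0.034 to between 0.056 and 0.222 if only placebo loses subjects, and the other way if only active does. A rescue-window rule could lower or raise power from 34%. The consequence is limited to how these tertiary results can be read, so this is a worthwhile clarification and not a threat to the trial's main conclusions.

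**What to change.** 1. Make the first-request row in Tables 14.2.2.4-2 and 14.2.2.5-2 descriptive, with no least squares mean difference, CI or p-value.
2. In Table 14.2.2.9-2 use the efficacy analysis set as the denominator. Count subjects withdrawn before the time point for lack of efficacy as not pain free. State the rule for other withdrawals and for intermittent missing scores, and say that actual scores are used.
3. Beside the raw proportion, show a supplementary version that counts a score inside a SAP 7.1.2 rescue window as not pain free, with a note that PCA interval data make some windows approximate.

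The cost is SAP wording and table programming, with no new data and one extra display. Proportions will be the same or lower in both arms. The change should be made before Part 2 is unblinded.
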